3.6 Statistics

3.6.1 Calculation of sample size

The calculation of the sample size is based on the measurement of the primary outcome. The primary outcome is the change of PUQE score on day 15 at the end of the treatment when compared with the baseline.

The change of PUQE score from baseline is used to compare the efficacies between the TN group and the sham TN group. Since there are no randomized controlled trials

of TN for the treatment of VNP, this project hypothesizes that TN can achieve the same efficacy as acupuncture, and the sample size is calculated according to the effect of acupuncture in the references [7], assuming that the PUQE score decreased by 4.9 points from baseline with a standard deviation of 2.4 after TN treatment, and the PUQE score also decreased by 4 points from baseline with a standard deviation of 2.7 after sham TN, the combined variance was 2.0, and the $\alpha = 0.05$ (bilateral), $\beta = 0.20$, and power = 0.80 were taken to allocate each group according to 1:1, and the statistical sample size was 128 cases in each group. Considering factors such as dropout/rejection, the number of enrolled cases was increased by 20%, and 160 subjects in each group were planned to be enrolled, with a total of 320 cases.

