3.1 The selection and exclusion of subjects

We will choose moderate or severe 320 VNP patients who take a visit during Oct. 2024 to Oct. 2028 to the departments mentioned below: Department of Integrated Traditional Chinese and Western Medicine, Tongji Hospital, Tongji Medical College, Huazhong University of Science and Technology, Wuhan, Hubei, China; Fujian Provincial Maternal and Child Health Care Hospital; Jingzhou Traditional Chinese Medicine Hospital, Jingzhou, Hubei, China; Qianjiang Maternal and Child Health Care Hospital, Qianjiang, Hubei, China; Xiaogan Maternal and Child Health Care Hospital, Xiaogan, Hubei, China; Qianjiang Central Hospital, Qianjiang, Hubei, China; Shiyan People's Hospital, Shiyan, Hubei, China; Wuhan Jinxin Gynecology

and Obstetrics Hospital of Integrative Medicine, Wuhan, Hubei, China; Xiangyang Traditional Chinese Medicine Hospital, Xiangyang, Hubei, China; Suizhou Maternal and Child Health Care Hospital, Suizhou, Hubei, China; Nanzhang County Traditional Chinese Medicine Hospital, Nanzhang, Hubei, China; Dongchangfu District Maternal and Child Health Care Hospital of Liaocheng City, Liaocheng, Shandong, China; Xiangyang Central Hospital, Xiangyang, Hubei, China; Aksu Prefecture Maternal and Child Health Hospital, Aksu, Xinjiang, China.

The age of the patients is between 20 to 45 years. According to the Network version of the central randomization system, patients are allocated randomly as 1:1 to TN group, sham TN group and blank control group with 160 patients in each group. The network version of the central randomization system designs the random parameters. The clinical researchers log in the system and input the information of the subjects to be enrolled, after that they can obtain the random number and grouping information assigned by the system. The randomization protocol and the parameters set during the generation of the protocol are collectively called blind substrates, and are all kept by people who are not involved in the process of treatment, evaluation and statistical analysis.

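### Three groups of 160 make 480, but the protocol gives the total as 320; a three-arm trial stopped at 320 would have about 73% power before dropout and 63% after it, not 80%.

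*Protocol*

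**What the plan says.** Section 3.1 opens with the recruitment figure: "We will choose moderate or severe 320 VNP patients". The following paragraph describes the allocation: "patients are allocated randomly as 1:1 to TN group, sham TN group and blank control group with 160 patients in each group".

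Section 3.6.1 sizes the trial on the day-15 change in PUQE score, "to compare the efficacies between the TN group and the sham TN group". The assumptions are that "the PUQE score decreased by 4.9 points from baseline with a standard deviation of 2.4 after TN treatment" and that "the PUQE score also decreased by 4 points from baseline with a standard deviation of 2.7 after sham TN". It adds that "the combined variance was 2.0". With two-sided alpha 0.05 and 80% power it arrives at 128 per group, allows 20% for dropout, and concludes that "160 subjects in each group were planned to be enrolled, with a total of 320 cases".

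The blank control group is a full arm elsewhere. Section 3.2 describes its care, section 3.2.3 its records, and section 3.6.2 compares the primary outcome across three groups.

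**The concern.** The two totals cannot both hold. Three groups of 160 need 480 women, and 320 is two groups of 160. The likeliest explanation is that a two-group calculation was doubled and the blank control arm never added. The two-part ratio 1:1, which section 3.1 applies to three arms, points the same way, but the protocol does not confirm this.

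The total is the number that sites, the ethics committee and the central randomisation system work to, and 320 is the only total stated. If recruitment ends there with three equal arms, each arm falls below the 128 evaluable women that the protocol says it needs, even with no dropout. A null result for TN versus sham would then be hard to interpret. If recruitment runs to 160 per arm, the trial enrols 50% more pregnant women than its stated total.

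A second, smaller fault sits in the same paragraph: the combined variance of 2.0 does not follow from the SDs printed beside it.

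**Working it through.** **Inputs, all from section 3.6.1 unless noted.** Mean falls of 4.9 (TN) and 4.0 (sham), so the difference is 0.9; SDs 2.4 and 2.7; alpha 0.05 two-sided; power 0.80; dropout allowance 20%; 160 enrolled per group; total 320. Three groups: section 3.1.

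**Step 1. Pooled variance.** (2.4² + 2.7²)/2 = (5.76 + 7.29)/2 = 6.525, so the pooled SD is √6.525 = 2.554. The stated value is 2.0.

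**Step 2. Reproducing the 128.** Normal approximation: n = 2 × 6.525 × (1.960 + 0.842)² / 0.9² = 126.5, so 127 per group. The two-sample t-test (noncentral t) gives 127.4, so 128 per group, which matches the protocol.

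The stated 2.0 does not give 128 under either reading (t-test):

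| Variability used | n per group |
|---|---|
| SDs 2.4 and 2.7 (pooled SD 2.554) | 128 |
| 2.0 read as an SD | 79 |
| 2.0 read as a variance (SD 1.414) | 40 |

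**Step 3. Dropout.** 128/(1 − 0.20) = 160, which matches. This reads the allowance as a 20% loss from those enrolled. A literal 20% increase would be 128 × 1.2 = 153.6, or 154, so the 160 shows that the loss reading was used.

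**Step 4. Total.** 3 × 160 = 480; 2 × 160 = 320; the gap is 160.

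**Step 5. Power for TN versus sham if 320 is shared equally by three arms.** 320/3 = 106.7 per arm; after 20% loss, 106.7 × 0.8 = 85.3. With noncentrality 0.9 / (2.554 × √(2/n)):

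| Evaluable per arm | Noncentrality | Power (t) | Power (normal) |
|---|---|---|---|
| 128 (160 enrolled, 20% lost) | 2.82 | 80.2% | 80.5% |
| 106.7 (320/3, no loss) | 2.57 | 72.6% | 73.0% |
| 85.3 (320/3, 20% lost) | 2.30 | 62.9% | 63.4% |

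No multiplicity adjustment is applied, because the protocol's calculation concerns one comparison at two-sided 0.05.

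**The case against.** The strongest reply is that no passage plans 107 per group. Sections 3.1 and 3.6.1 both fix 160 per group, and at that size power is 80.2% after the planned losses. Section 3.6.1 is explicitly a TN-versus-sham calculation, so within it a 1:1 ratio and 2 × 160 = 320 are correct for the two powered groups. That stands as an account of how the figure probably arose. It does not rescue section 3.1, which gives 320 as the number recruited to the trial and then divides the patients among three arms of 160. It does mean that the power loss is conditional on stopping at 320.

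The 63% can also be called pessimistic. PUQE is scored on days 3, 6, 9, 12 and 15, and section 3.6.2 imputes missing scores for women who withdraw, so earlier scores may recover some information. That is fair: in the 320 scenario the 63% counts completers only, and actual power could lie between 63% and 73%. However, the protocol's own inflation from 128 to 160 treats dropouts as lost, so 63% is the figure on the same basis as the stated 80%.

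Finally, the variance of 2.0 did not drive the sample size, since 128 follows from the SDs. This is correct; it is a reporting error and the lesser of the two faults.

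**Conclusion.** The concern holds. The planned total is wrong as written: 320 against 3 × 160 = 480, a discrepancy of one whole arm, found within section 3.1 and repeated in section 3.6.1. The per-group figures of 128 and 160 reproduce and need no change.

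If 160 per group are enrolled, the 80% power stands. If recruitment stops at 320 with equal allocation to three arms, power for TN versus sham is about 73% without losses and about 63% with the planned 20% loss. These figures assume the protocol's difference of 0.9 and its SDs of 2.4 and 2.7, the inputs that give 128, with two-sided alpha 0.05 and no multiplicity adjustment. The stated combined variance of 2.0 should be 6.525 (SD 2.55). The total must be corrected because it is a core figure of the trial.

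**What to change.** The sponsor should first state which number is operative, then make both sections agree.

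- **If 160 per group is intended:** give the total as 480 (3 × 160) in sections 3.1 and 3.6.1, and the allocation in section 3.1 as 1:1:1. The 1:1 in section 3.6.1 may stay if it is labelled as the TN-versus-sham calculation.
- **If 320 is the true limit:** state about 107 enrolled and about 85 evaluable per group, change 160 accordingly in both sections, correct the ratio in section 3.1 to 1:1:1, and restate the power for TN versus sham as about 73% before and 63% after 20% loss.
- **In either case:** replace the combined variance of 2.0 with a pooled SD of 2.55 (variance 6.5).

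If sites and the randomisation system already work to 160 per group, the first option costs only protocol wording. If they work to 320, moving to 480 means 160 more participants and is a real amendment; the protocol does not show which applies. Keeping 320 adds no recruitment, but the trial must then declare lower power.

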3.6.2 Statistical test

The method of intention analysis set is used to detect the difference of the change of PUQE scores among three groups. Persenka square test is used to compare the live yield of the main index. The secondary indicators are analyzed by the corresponding statistical methods (Chi-Square test is used for counting data, and t test is used for measuring data with equal variance). The primary outcome was analyzed according to the intention-to-treat (ITT) principle. Chained multiple imputation under the missing-at-random assumption was used to generate 20 imputed data sets for missing PUQE scores over the intervention period in participants who withdrew (MI procedure in SAS), and the estimates were combined using the Rubin rules (MIANALYZE procedure in SAS) across the imputed sets. The modified ITT population was defined as the participants who completed the primary outcome measurement. The per protocol set (PPS) referred to participants who adhered to the treatment protocol they were originally allocated to.

Reference

- [2] Ding XJ. Nausea and vomiting of pregnancy and its associations with postpartum depression in pregnant women in Wuhan [D]. Wuhan: Huazhong University of Science and Technology, 2021. (Artical in Chinese)
- [5] Committee on Practice Bulletins-Obstetrics. ACOG Practice Bulletin No. 189: Nausea and vomiting of pregnancy [J]. Obstet Gynecol, 2018, 131(1): e15-e30.
- [6] Catherine Nelson-Piercy, Caitlin Dean, Manjeet Shehmar, Roger Gadsby, Margaret O'Hara, Kenneth Hodson, Melanie Nana. The Management of Nausea and Vomiting in Pregnancy and Hyperemesis Gravidarum (Green-top Guideline No. 69). BJOG, 2024; 131(7): e1-e30.

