RCTs are still needed to provide high-quality evidence-based evidence. This project intends to use multi-center, large-sample, randomized, controlled, double-blind clinical trials to observe the effects of nausea and vomiting, quality of life, anxiety and depression, weight change, blood electrolyte levels, liver and kidney function, thyroid function, intravenous infusion therapy, use of additional drugs, hospitalization, pregnancy complications (gestational diabetes and hypertensive diseases), pregnancy outcomes and neonatal outcomes in women with VNP, and evaluate their safety, so as to provide high-quality evidence support for the clinical promotion and application of needles in the treatment of VNP.

2. Study objectives

A multicenter, large-sample, randomized, controlled, double-blind clinical trial was conducted to observe the effects of TN on nausea and vomiting, quality of life, anxiety and depression, weight change, blood electrolyte levels, liver and kidney function, thyroid function, intravenous fluid therapy, use of additional drugs, hospitalization, pregnancy complications, pregnancy outcomes, and neonatal outcomes in women with VNP, and to evaluate its safety.

3. Study content

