3.2 The intervention program

According to the theory of traditional Chinese medicine, the treatment plan of TN is formulated, and the study protocol follows the CONSORT and STRICTA regulations, and details the number of TN used, the frequency of treatment and the duration of treatment. Both the TN group and the sham TN group were treated with a fixed treatment regimen, which was treated once every 3 days, for a total of 5 treatments for 15 days. During the same period, the blank control group was not given TN or sham TN treatment. All three groups of patients were given pregnancy care and dietary guidance.

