3.2.3 Record for the treatment

The treatment date, time and the name of the acupuncturist are recorded when the patient receives TN or sham TN treatment. No treatment is given to the blank control group, but the date and times of the inquiry of blank control group are also recorded. During the treatment, the local hematoma or turquoise, pain or skin allergies that may occur during the treatment, as well as other discomforts after the treatment (nausea, vomiting, palpitations, dizziness, headache, anorexia and insomnia), should be recorded in detail and disposed in time.

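### The trial is sized for TN versus sham TN, but the primary analysis is stated as a difference among three groups, so a positive result could come from the unblinded blank arm alone

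*Protocol*

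**What the plan says.** Section 3.6.1 defines the outcome, "The primary outcome is the change of PUQE score on day 15 at the end of the treatment when compared with the baseline", and states its use: "The change of PUQE score from baseline is used to compare the efficacies between the TN group and the sham TN group". The only alpha (0.05, two-sided) and the only power (0.80) in the protocol belong to that two-group comparison.

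Section 3.6.2 then states the analysis of the same outcome: "The method of intention analysis set is used to detect the difference of the change of PUQE scores among three groups". It gives no test, no primary pair and no order of comparisons.

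There are three arms. Section 3.1 says that "patients are allocated randomly as 1:1 to TN group, sham TN group and blank control group with 160 patients in each group". Section 3.2 says that "the blank control group was not given TN or sham TN treatment", and section 3.2.3 repeats it: "No treatment is given to the blank control group". Section 2 nevertheless describes the whole trial as double-blind: "A multicenter, large-sample, randomized, controlled, double-blind clinical trial was conducted to observe the effects of TN on nausea and vomiting".

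**The concern.** Two adjacent sections put different questions to one primary outcome. Section 3.6.1 asks whether TN beats sham. Section 3.6.2 asks whether any of three groups differ.

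The blank group makes the difference matter. Its participants know that they received no device, and the PUQE score consists of three questions about the patient's own symptoms (Table 1 in section 3.1.1.2). Only TN versus sham can be a blinded comparison. An overall three-group test can be significant because the open arm reports less improvement, with no difference between TN and sham. Such a result would fit the wording of 3.6.2 without answering the question the trial was sized for.

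**Working it through.** **Inputs from section 3.6.1.** Mean decrease 4.9 (SD 2.4) on TN and 4.0 (SD 2.7) on sham; two-sided alpha 0.05; power 0.80; 128 evaluable and 160 enrolled per group.

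**Assumed.** The blank-arm mean decrease, which the protocol does not give, is varied over a range. All arms share one SD.

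**Step 1: reproduce the plan's figure.**
- Pooled variance = (2.4² + 2.7²)/2 = 6.525, so SD = 2.554.
- Normal approximation: n = 2 × 6.525 × (1.960 + 0.842)² / 0.9² = 126.5, rounded up to 127.
- Exact two-sample t test: 128 per group, power 80.2% (noncentrality 0.9 / (2.554 × √(2/128)) = 2.82).
- Dropout: 128 / 0.8 = 160.

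The plan's 128 is therefore a two-group figure for TN versus sham. The combined variance of 2.0 also stated there does not give 128: as a variance it gives 39 per group, and as an SD it gives 78. SD 2.554 is used below because it reproduces the plan.

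**Step 2: overall test when TN equals sham.** One-way F test with 2 and 381 degrees of freedom, noncentrality λ = n Σ(μᵢ − μ̄)² / SD². If TN = sham = 4.0 and the blank arm is lower by d, then λ = 128 × (2/3) × d² / 6.525. The last column is by simulation.

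| Blank shortfall d | λ | Overall test significant | TN vs sham test significant | Share of significant overall tests in which TN vs sham is not significant |
|---|---|---|---|---|
| 0 | 0 | 5.0% | 5% | 50% |
| 0.25 | 0.82 | 11.6% | 5% | 73–74% |
| 0.5 | 3.27 | 34.5% | 5% | 88% |
| 0.9 | 10.59 | 83.5% | 5% | 94% |
| 1.5 | 29.43 | 99.9% | 5% | 95% |

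**Step 3: overall test under the planned effect** (TN 4.9, sham 4.0). The last column is by simulation.

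| Blank mean decrease | λ | Power of overall test | Power of TN vs sham tested only after a significant overall test |
|---|---|---|---|
| 4.45 (midway) | 7.94 | 71.1% | 70% |
| 4.0 (equal to sham) | 10.59 | 83.5% | 76% |
| 3.75 | 14.35 | 93.2% | 79% |
| 3.5 | 19.75 | 98.4% | 80% |
| 3.1 | 31.78 | above 99.9% | 80% |

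The power of the overall test depends on a quantity the plan never specifies. A direct TN-versus-sham test has 80.2% in every row.

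**Step 4: dependence on the total.** The 80.2% needs 128 evaluable per arm. Section 3.6.1 says "160 subjects in each group were planned to be enrolled, with a total of 320 cases", while three arms of 160 make 480. If 320 covered all three arms, 320/3 ≈ 107 enrolled, less 20%, leaves about 85 evaluable per arm, and TN-versus-sham power falls to 62.7%.

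**The case against.** The strongest reply is that 3.6.2 names no F test or other overall test. Its sentence is awkward and is mainly about the analysis population, and the phrase about three groups could equally mean pairwise comparisons. Section 3.6.1 already names TN versus sham, and the specific statement should govern the general one. The named test, the order of tests and multiplicity can be left to the statistical analysis plan. The blank-arm figures are assumed, and the 84% and 99.9% are correct rejections of a false hypothesis (the blank arm really does differ), not false positives.

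Much of this stands as a limit. The overall-test reading is not the only one, the blank-arm inputs are assumptions, and the overall test keeps its 5% error when all three arms are equal. It also has more than 80% power in most scenarios shown. If TN versus sham is tested after a significant overall test, little power is lost once the blank arm is 0.25 to 0.5 points worse than sham.

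The conflict remains. Under a pairwise reading the deciding pair is still unnamed in 3.6.2, and three unadjusted t tests would give at least one significant result in about 12% of trials with all arms equal. A follow-up test would protect the TN claim, but 3.6.2 states none. A statistical analysis plan cannot settle this quietly: if it makes the three-group difference the primary test it departs from 3.6.1, and if it tests TN versus sham alone it departs from the wording of 3.6.2.

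**Conclusion.** The point holds and should be fixed. The stated alpha and power belong to TN versus sham, and the stated analysis does not carry that contrast over. The main harm is to interpretation: with no TN–sham difference, an overall test would be significant in 12% to 99.9% of trials for assumed blank-arm shortfalls of 0.25 to 1.5 points. In roughly three quarters or more of those trials TN versus sham would not itself be significant. The effect on power can go either way, from 71% to above 99.9% against the planned 80%. These figures rest on SD 2.55, 128 evaluable per arm, an assumed blank-arm response, and 3.6.2 being read as an overall test. That the two sections disagree does not depend on any of these.

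**What to change.** In section 3.6.2, replace the sentence on the difference among three groups with:

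*The primary analysis compares TN with sham TN in the change of PUQE score from baseline to day 15 (ITT, two-sided 0.05, estimated in each imputed data set and pooled by Rubin's rules). Comparisons with the blank control group and any overall three-group test are secondary and cannot by themselves support the primary claim.*

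How the secondary comparisons are tested can be left to the statistical analysis plan; testing TN versus blank only after a significant primary test is one acceptable option.

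The cost is two sentences, with no new data or visits and no change in the number per arm. The small downside is that TN versus blank leaves the primary claim. The planned 80% is kept only with 160 enrolled per arm, 480 in total, so the stated total of 320 has to be reconciled as a separate correction.

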3.1.1.2 Women diagnosed with moderate to severe NVP in the first trimester: the

severity of NVP was determined by the PUQE score (see Table 1), and the PUQE score ranged from 3 ~ 15, < 6 was mild NVP, 6 ~ 12 was moderate NVP, and ≥ 13 was severe NVP. PUQE score ≥ 6 may be included in this study;

3.1.1.3 Women voluntarily sign the informed consent form.

Table 1 Quantification of NVP in the US ACOG guidelines

1. In general, how often do you feel nauseous or nauseous each day?				
Never (1)	≤ 1 h (2)	2~3 h (3)	4~6 h (4)	> 6 h (5)
2. In general, how many times a day do you vomit?				
Never (1)	1~2 (2)	3~4 (3)	5~6 (4)	≥ 7 (5)
3. In general, how many times a day do you retch (no contents) ?				
Never (1)	1~2 (2)	3~4 (3)	5~6 (4)	≥ 7 (5)

Total score (add all the points together): Mild NVP: < 6 , moderate NVP: $6 \sim 12$, severe NVP: ≥ 13

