3.3 Outcome measures

3.3.1 Primary outcome measure

PUQE scores were evaluated before treatment and on days 3, 6, 9, 12, and 15 of treatment. The primary outcome measure was the change of PUQE score on day 15 at the end of the treatment when compared with the baseline.

3.3.2 secondary efficacy endpoints

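### The primary comparison is specified and sized as PUQE change with no baseline adjustment, which forgoes a likely and almost free gain in precision

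*Protocol*

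**What the plan says.** Section 3.3.1 defines the endpoint: "The primary outcome measure was the change of PUQE score on day 15 at the end of the treatment when compared with the baseline". It also shows that a baseline value is available for every patient: "PUQE scores were evaluated before treatment and on days 3, 6, 9, 12, and 15 of treatment".

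Section 3.6.1 carries the change score into the sample size: "The change of PUQE score from baseline is used to compare the efficacies between the TN group and the sham TN group". It assumes mean falls of 4.9 (SD 2.4) with TN and 4.0 (SD 2.7) with sham, two-sided alpha 0.05 and 80% power, and arrives at 128 per group.

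Section 3.6.2 uses the intention-to-treat set "to detect the difference of the change of PUQE scores among three groups". It then fixes the imputation method, 20 imputed data sets, pooling by Rubin's rules, the SAS procedures and the analysis sets. It names no test, model or covariate for the primary comparison. For continuous secondary indicators it does name a method: "t test is used for measuring data with equal variance".

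Section 3.1.1.2 states the scale ("the PUQE score ranged from 3 ~ 15") and the entry threshold ("PUQE score ≥ 6 may be included in this study").

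**The concern.** A raw change score does not take out the influence of the starting value. On this scale the starting value matters by construction, because nobody can fall below 3. A woman who enters at 6 can improve by 3 points at most, which is less than either mean fall assumed in section 3.6.1. A woman who enters at 15 can improve by up to 12. Part of the spread in change is therefore likely to reflect where women started and not what treatment did.

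If that spread is left in the comparison, the standard error is larger than it need be, and any chance difference in baseline PUQE between the groups feeds into the observed difference in change. The planned TN versus sham difference is only 0.9 points, so precision is worth having. The same reasoning applies to NVPQOL, SAS, SDS and PSQI, which section 3.3.2.1 has measured before and after treatment, and to weight change in section 3.3.2.2.

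**Working it through.** **1. Reproduce the planned size (inputs from section 3.6.1).**
- Difference: 4.9 − 4.0 = 0.9.
- Pooled variance of change: (2.4² + 2.7²)/2 = (5.76 + 7.29)/2 = 6.525, so SD = 2.554.
- n per group = 2 × (1.960 + 0.842)² × 6.525 / 0.9² = 127 by the normal approximation, and 128 with the t distribution.
- The stated 128 is therefore an ordinary two-sample comparison of change with no covariate.
- The combined variance of 2.0 printed beside it does not give 128: n would be 39 if 2.0 is a variance and 78 if it is an SD. That is a separate matter, and the SDs of 2.4 and 2.7 are used here.

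**2. Power without adjustment at 128 per group.**
- Variance of the difference: 2 × 6.525/128 = 0.102, so SE = 0.319.
- Power = Φ(0.9/0.319 − 1.96) = 0.805. The plan's 80% is met.

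**3. Power with baseline as covariate.** The protocol gives neither the baseline SD nor the correlation r between baseline and day-15 PUQE. Assume the same SD, s, at both times.
- Variance of change = 2s²(1 − r).
- Residual variance after adjustment = s²(1 − r²).
- Ratio = (1 + r)/2.

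Holding the change variance at 6.525:

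| r (assumed) | Ratio | Implied s | Power at 128 per group | n per group for 80% power (normal approximation) |
|---|---|---|---|---|
| no adjustment | 1 | – | 0.805 | 127 |
| 0.3 | 0.65 | 2.16 | 0.938 | 83 |
| 0.5 | 0.75 | 2.55 | 0.902 | 95 |
| 0.7 | 0.85 | 3.30 | 0.864 | 108 |

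**4. Without the equal-SD assumption.** In general the ratio is 1 − c², where c is the correlation of change with baseline.
- c = 0: ratio 1, power 0.805, no gain.
- c = −0.3: ratio 0.91, power 0.840, n = 116.
- c = −0.5: ratio 0.75, power 0.902, n = 95.

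**5. Is chance imbalance a further loss?** Take r = 0.3.
- The SE of the baseline difference is 2.16 × √(2/128) = 0.27.
- An imbalance of one SE shifts the difference in change by (1 − 0.3) × 0.27 = 0.19 points, which is 21% of 0.9.
- The gap between the unadjusted and adjusted variances is 0.102 − 0.65 × 0.102 = 0.036, and √0.036 = 0.19.

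The two figures agree. The imbalance shift is already inside the larger unadjusted standard error and must not be counted again. At r = 0.7 the shift is 0.3 × 3.30 × 0.125 = 0.12 points, or 14% of 0.9.

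**The case against.** The strongest objection is that section 3.6.2 does not say the primary analysis is unadjusted. It names no model, a change endpoint is compatible with analysis of covariance, and the covariate list of a primary model is often left to a statistical analysis plan, which is not shown here. A reader might infer that the protocol prescribes an unadjusted test of PUQE change, or that its t test governs the primary outcome. The text supports neither: the t test is attached to the secondary indicators only. What remains is that the comparison is described and sized as raw change, and that a section detailed enough to fix the number of imputations, the pooling and the analysis sets never mentions baseline. For the continuous secondary outcomes the unadjusted test is named outright.

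A reader might also infer that the trial is underpowered or biased without adjustment. It is not on this account. The 128 per group was derived from the SDs of change and gives its 80%. Under randomisation an unadjusted comparison of change is valid and unbiased on average; chance imbalance shifts a particular result, and its standard error already allows for that.

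The size of the gain is also open to challenge. Entry at 6 or more truncates baseline, while day-15 scores can go down to 3, so equal SDs are doubtful. With r = 0.7 the implied baseline SD of 3.30 exceeds even a uniform spread over 6 to 15 (√((10² − 1)/12) = 2.87). If r times the day-15 SD equals the baseline SD, there is no gain at all. This stands, and it is why the gain is given as a range that reaches down to zero.

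**Conclusion.** The point holds as a free improvement. The protocol specifies and sizes its primary comparison as change in PUQE without using a baseline value that it already collects and that limits how far each woman can fall.

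What is forgone is precision. Under equal SDs and r between 0.3 and 0.7, power at 128 evaluable per group would be about 0.94 to 0.86 instead of 0.80; the gain shrinks to nothing as the correlation of change with baseline approaches zero. The cap on the possible fall makes some dependence likely but does not fix its strength. Greater precision and protection from chance imbalance are one gain, not two.

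These figures take 128 evaluable per group as section 3.6.1 states. They make no use of the separate conflict between a total of 320 and three groups of 160.

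**What to change.** In section 3.6.2, state that the primary analysis is a linear model of day-15 PUQE (or its change) on treatment group with baseline PUQE as covariate, fitted in each of the 20 imputed data sets and pooled by Rubin's rules, and that the adjusted TN minus sham difference is reported with its 95% confidence interval. With baseline as a covariate, day-15 score and change give the same treatment estimate, so the endpoint in section 3.3.1 need not be redefined. Use the same form of model, with each outcome's own baseline, in place of the t test for NVPQOL, SAS, SDS, PSQI and weight. If a statistical analysis plan already names such a model, a cross-reference is enough.

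The cost is one or two sentences, with no extra patients, visits or measurements. The wording should be settled before unblinding, so that there is no later choice between adjusted and unadjusted results.
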